10.3 Part B Analysis Plan

Sample size consideration:

The clinical trial will employ a one-stage design (A'Hern, 2001). In each molecularly defined positive cohort, the study requires 12 subjects to decide whether the ORR is greater than or equal to 0.400 assuming the response rate is 0.050 without treatment. 12 subjects will provide over 90% power to detect this rate difference with a targeted type I error rate of 0.05 and an actual error rate of 0.02. If the number of responses is 3 or more, the hypothesis that $P \leq 0.05$ (null hypothesis) is rejected. If the number of responses is 2 or less, the hypothesis that $P \geq 0.40$ is rejected. Note, given the exploratory nature of this phase II clinical trial, p-values will not be adjusted for multiple outcomes in the primary objective.

We will also include a pan-negative cohort of 20 patients to compare the ORR between each positive cohort and the negative one as secondary objectives. The ORR response differences between each biomarker positive cohort and the negative cohort will be evaluated using Fisher's exact test with a descriptive p-value. For *FGFR1* SISH+ or ISH+, the positive cohorts will also be combined for more power when comparing to the negative cohort. The response rates in different molecularly defined cohorts and different dose cohorts will be summarized using binomial proportions with 95% exact binomial confidence intervals. Differences among cohorts will be evaluated using Fisher's exact test with a descriptive p-value.

Another role of the double negative cohort is to permit rapid patient accrual to assess the PD/dose determination markers early in the conduct of the study, being expanded as needed if doses other than 45mg QD have to be explored. In addition, it may generate 'atypical' *RET* and *FGFR1* negative responders, to be further explored in future.

The proportion of the initial 12 patients at 45mg QD (and in the 12 patients at any subsequent dose levels) demonstrating a $\geq 50\%$ increase in plasma FGF23 by Day15 (defined as a 'PD-response') will be assessed in the same statistical manner as radiographic responses in order to determine whether the dose/regimen used is affecting the FGFR pathway in normal tissues. A $\geq 50\%$ increase in plasma FGF23 measurements occurring in ≥ 3 of 12 patients will be considered indicative of FGFR inhibition (Shi et al,

2009). In addition, FGFR inhibition should be accompanied with a decrease in the fractional excretion of phosphorus in the urine (normal: 10-15%) and an elevation of serum phosphorus compared to baseline at the same time. If exposures are inadequate to affect these biomarkers (provided no evidence of tumor shrinkage has occurred in any of the FGFR+ cohorts by that point), due to the new data on risk factors associated with ponatinib, higher doses/dosing regimens of ponatinib will not be explored, however, if 45mg is not tolerable, but there is insufficient evidence to assess efficacy, 30mg will be considered for exploration in the FGFR-related cohorts. RET patients will commence at 30mg from the start due to the higher potency for ponatinib towards RET. A dose level will be considered tolerable following completion of 1 cycle (28 days) in 9 of 12 patients in the absence of dose limiting toxicity (DLT). If ≥ 3 patients experience DLT at this dose level, the dose level will be deemed non-tolerated.

If doses other than 45mg QD have to be explored, the number of patients in each biomarker selected cohort will be modified to include only those treated at the final 'biologically selected dose' (i.e. the dose associated with evidence of FGFR pathway PD modulation or of radiographic responses in FGFR+ cohorts) and the response rates in each biomarker selected cohort will be calculated within each cohort using only the number treated at this dose. The number of adverse events and percentages will be tabulated per organ and per visit. Kaplan-Meier survival curves will be used to display PFS and extra-CNS PFS (Camidge et al, 2011; Lin et al, 2012). Progression-free median time and 95% confidence interval will be reported. Proportions of failure due to CNS or extra-CNS will be reported along with 95% exact confidence intervals. Response duration will be summarized using median and range (min, max). Where biomarker overlap occurs, exploratory analyses of the differential effect of one biomarker over another will be explored across patients in all cohorts using multivariate analysis. Exploratory analyses will include assessing the impact of different SISH+ patterns, of higher cutpoints for FGFR1 SISH and ISH and the impact of FGF ligand levels on maximal percentage shrinkage per RECIST or PFS or duration of response in the FGFR1 SISH/ISH+ cohorts.

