responses are seen in the initial RET+ cohort but FGFR1+ responses or FGFR PD modulation have been noted at 45mg and 45mg appears acutely well tolerated per DLT criteria we will reconsider this logic and accrue an additional RET+ cohort at 45mg. If doses other than 45mg QD are explored, the number of patients in each biomarker selected cohort will be modified to include only those treated at the final ‘biologically selected dose’ (i.e. the tolerable dose associated with evidence of FGFR pathway pharmacodynamic modulation or of radiographic responses in FGFR biomarker selected cohorts) and the response rates in each biomarker selected cohort will be calculated within each cohort using only the number treated at this dose.

Objectives:

Primary:

Part A – To determine the prevalence of defined biomarkers in the screened patient populations.

Part B – To determine the objective response rate (ORR) (RECIST v1.1) to ponatinib at a ‘biologically selected dose’ in different molecularly defined cohorts of lung cancer.

Secondary:

Part A –

- 1) To determine the effectiveness of prescreening locally and nationally.
- 2) To determine the clinical and pathological features associated with biomarker positivity and negativity.

Part B –

- 1) To evaluate the safety, tolerability, and adverse event profile of ponatinib in patients with advanced lung cancer.
- 2) To determine the progression free survival (PFS), pattern of failure (CNS vs. extra-CNS) and response duration (in patients who achieve an objective response) of ponatinib in molecularly defined cohorts of patients with advanced lung cancer treated at the ‘biologically selected dose’.
- 3) To compare the ORR in biomarker positive cohorts to the FGFR1 double negative cohort.

Tertiary/Exploratory:

- 1) To explore additional molecular mechanisms of initial sensitivity and resistance to ponatinib in patients with advanced lung cancer, including but not limited to addressing the impact of higher cutpoints/alternate patterns of FGFR1 copy number by SISH and mRNA levels by ISH on maximal percentage shrinkage per RECIST or PFS or duration of response in the FGFR1 copy number and/or mRNA positive cohorts; and the impact of FGF2 and/or 9 ligand mRNA levels by ISH on maximal percentage shrinkage per RECIST or PFS or duration of response in FGFR1 copy number and/or mRNA positive cohorts.

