2.2.2 Updated long term risks associated with ponatinib use

Arterial and venous thrombosis and occlusions, including fatal myocardial infarction, stroke, stenosis of large arterial vessels of the brain, severe peripheral vascular disease, and the need for urgent revascularization procedures have occurred in at least 27% of ponatinib-treated patients from the phase 1 and phase 2 trials. Ponatinib can cause fatal and life-threatening vascular occlusion within 2 weeks of starting treatment. Ponatinib can also cause recurrent or multi-site vascular occlusion.

In the dose-escalation (phase 1) clinical trial, 48% (31/65) of patients with CML or Ph+ ALL developed vascular occlusive events. The median time to onset of the first vascular occlusion event was 5 months.

Ponatinib can cause fatal and life-threatening vascular occlusion in patients treated at dose levels as low as 15 mg per day. Patients with and without cardiovascular risk factors, including patients age 50 years or younger, experienced these events. Vascular occlusion adverse events were more frequent with increasing age and in patients with prior history of ischemia, hypertension, diabetes, or hyperlipidemia.

Arterial Occlusion and Thrombosis

Arterial occlusion and thrombosis occurred in at least 20% (91/449) of Ponatinib-treated patients with some patients experiencing events of more than one type. Patients have required revascularization procedures (cerebrovascular, coronary, and peripheral arterial) due to vascular occlusion from Ponatinib. Cardiac vascular occlusion, including fatal and life-threatening myocardial infarction and coronary artery occlusion has occurred in 12% (55/449) of Ponatinib -treated patients, Patients have developed heart failure concurrent or subsequent to the myocardial ischemic event.

Cerebrovascular occlusion, including fatal stroke has occurred in 6% (27/449) of Ponatinib -treated patients. Ponatinib can cause stenosis over multiple segments in major arterial vessels that supply the brain (e.g., carotid, vertebral, middle cerebral artery).

Peripheral arterial occlusive events, including fatal mesenteric artery occlusion and life-threatening peripheral arterial disease have occurred in 8% (36/449) of Ponatinib -treated patients. Patients have developed digital or distal extremity necrosis and have required amputations.

Venous Thromboembolism

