- l. From Cycle 5 onwards, except EOS visit, study specific safety labs (Mg, Phosphorus, amylase, lipase and a blood lipid panel (Triglyceride, cholesterol, LDL, HDL)) only as clinically indicated.
- m. Treatment beyond progression may be permissible (see section 9). In the event of CNS progression, if CSF were to become available through standard of care procedures timed plasma and CSF relative to last dose of drug will be captured and sent to ARIAD for PK analysis. If treatment beyond progression occurs, documentation of the perceived reasons for ongoing clinical benefit is required. Study assessments will remain the same as if progression had not occurred (although if new CNS progression were noted, in a patient not previously known to have brain metastases, additional CNS surveillance is recommended). A 30 day post-study visit to assess unresolved ponatinib-related toxicities with laboratory tests to be ordered as clinically needed is recommended.
- n. In patients who are not already on a statin or anticoagulation (aspirin, heparin, coumadin or equivalent), in the absence of contraindications prophylaxis with 81mg aspirin QD and 10mg atorvastatin QD (or equivalent) is recommended to start the day after commencement of dosing with the ponatinib.

Part B First 12 patients treated at 45 mg QD	Screening (within 14 days of start of Rx; extra-CNS scans within 28 days of start of Rx; CNS imaging if not known CNS disease within 3 months of start of Rx, if known then within 28 days of start of Rx)	C1 D1	C1 D8 ^a	C1 D15 ^a	C2 D1	Day 1 of each Cycle ^l	First progression ^m
Informed consent/demographics/ medical history	X						
Ponatinib ⁿ	X (daily).....					
Concurrent meds	X	X	X	X	X	X	
Physical exam	X	X	X	X	X	X	X
Vital signs	X	X	X	X	X	X	X
Height	X						
Weight	X	X	X	X	X	X	X
Performance Status	X	X	X	X	X	X	X
CBC w/diff	X	X	X	X	X	X	X
CMP ^b , Mg, phos, LDH, amylase, lipase, lipid panel ^d	X ^c	X	X	X	X	X	X
Blood tumor marker ^c		X				X	X
Urine and blood for FGFR PD markers ^f		X	X	X	X		
PT/PTT, B-HCG ^g	X						
EKG and Echocardiogram	X						
Adverse event evaluation	X	X	X	X	X	X	X
Tumor measurements	X	Tumor measurements are repeated every 2 cycles					
Tumor specimen ^h	X ^h						X ^h
PG ^j		X					
Serum/plasma for biomarker banking ^k		X			X		X

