10.4 Efficacy and toxicity definitions

Evaluable for toxicity. All patients will be evaluable for toxicity from the time of their first treatment with ponatinib.

Evaluable for objective response. Only those patients who have measurable disease per RECIST v 1.1. present at baseline, have received at least one dose of drug, and have had their disease re-evaluated will be considered evaluable for response. These patients will have their response classified according to the definitions stated below.

Best overall response. The best overall response is the best response recorded from the start of the treatment until disease progression/recurrence (taking as reference for progressive disease the smallest measurements recorded since the treatment started). The patient's best response assignment will depend on the achievement of both measurement and confirmation criteria.

Duration of response. The duration of overall response is measured from the time measurement criteria are met for CR or PR (whichever is first recorded) until the first date that recurrent or progressive disease is objectively documented (taking as reference for progressive disease the smallest

measurements recorded since the treatment started). The duration of overall CR is measured from the time measurement criteria are first met for CR until the first date that recurrent disease is objectively documented. The duration of stable disease is measured from the start of the treatment until the criteria for progression are met, taking as reference the smallest measurements recorded since the treatment started.

Progression-Free Survival. PFS is defined as the duration of time from start of treatment to time of progression. Because of the potential for CNS progression to reflect PK rather than biological reasons for progression, where possible CNS and extra-CNS PFS will also be recorded.

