11.6 Data Management and Source Documentation

This protocol will adhere to the policies and requirements of the University of Colorado Cancer Center (UCCC) Institutional Data and Safety Monitoring Plan. The UCCC Data and Safety Monitoring Committee (DSMC) will serve as the DSMB. Toxicity data will be reviewed by the PI and the statistician after each of the first 12 patients across all cohorts at a given dose/schedule completes cycle 1 or experiences a DLT. This toxicity data will be analyzed for stopping rules and processed according to UCD/UCCC policy. PD data will be analyzed in conjunction with toxicity data to determine dose escalation per Section 9.

The investigator at each site is responsible for the collection and documentation of all study data. Source documents are the originals of any documents used to verify data entered on the CRF. Source documents verify the existence of a patient and support the inclusion of the patient in the study. Source documents must be legible and organized, and available for monitoring. Clinical records for all subjects studied including history and physical findings, laboratory data, and results of consultations are to be maintained by the investigator in a secure storage facility. These records are to be stored for at least seven years. It is the Investigator's responsibility to retain copies of the completed CRFs.

The investigator must ensure the anonymity of patients. The investigator will keep a Patient Master Log detailing each patient code and identifiers.

Data are to be recorded onto the CRFs. Corrections shall be made by approved personnel; the reasons for changes must be provided.

Any electronic data will be electronically loaded into the database and checked for validity.

The method of distribution and processes for data queries will be described in the study manual.

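### Section 10.3 gives no per-patient, time-based or exposure-adjusted analysis of vascular occlusive events, so the planned adverse event percentages cannot safely be set beside the historical 27-48%

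*Combined protocol and SAP*

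**What the plan says.** Safety is the first secondary objective of Part B: "To evaluate the safety, tolerability, and adverse event profile of ponatinib in patients with advanced lung cancer". Section 10.4 sets the population: "All patients will be evaluable for toxicity from the time of their first treatment with ponatinib". Section 10.3, and the matching synopsis paragraph, then give one sentence on how adverse events are summarised: "The number of adverse events and percentages will be tabulated per organ and per visit". No denominator, time scale, exposure measure or split by dose accompanies it. Exact intervals and summaries by dose cohort are specified for response rates only. The time-to-event method is kept for efficacy: "Kaplan-Meier survival curves will be used to display PFS and extra-CNS PFS".

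Other safety elements exist. The DLT rule covers one cycle: "A dose level will be considered tolerable following completion of 1 cycle (28 days) in 9 of 12 patients". Section 11.6 has the investigator and statistician review toxicity in the first 12 patients at each dose: "This toxicity data will be analyzed for stopping rules and processed according to UCD/UCCC policy". Section 11.1.3 lists vascular occlusive events as a single special-interest class, reportable within 2 business days whether serious or not. Section 11.9 sends a summary of AEs and SAEs to the DSMC every six months.

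On timing, Section 2.2.2 (updated long-term risks) says of the phase 1 trial: "The median time to onset of the first vascular occlusion event was 5 months". After treatment, calendar note m in Section 8.0 only recommends its visit: "A 30 day post-study visit to assess unresolved ponatinib-related toxicities".

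**The concern.** Vascular occlusion is the hazard that led to the amendment, the cap at 45mg and the 30mg start in the RET cohort. Section 2.3 argues that its median onset falls well after the 8-week efficacy scan, so that patients still on drug by then have been judged to benefit. The risk that matters is therefore the risk with continued dosing, and no planned analysis describes it.

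A percentage of treated patients reflects the hazard and also how long patients stayed on drug. If treatment is short, a low percentage may show little more than short exposure. Set beside the leukaemia figures, it could be read as evidence of a safer profile in lung cancer. Section 9.2 also contemplates exploring 30mg to find a safer long-term dose, yet no planned summary measures long-term vascular safety.

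**Working it through.** **Figures in the documents.** Section 2.2.2: 31/65 = 47.7% (stated as 48%) in phase 1, arterial events 91/449 = 20.3%, venous events 23/449 = 5.1%, and at least 27% across both trials. Treated total in Section 10.1: 22 + 4×13 = 74. These reproduce. The plan states no precision or sample-size figure for safety.

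**Assumptions.** A fraction F = 27% or 48% would have a vascular event with continued dosing. Onset is exponential with a median of 5 months. Patients stop the drug at an exponential rate with median m months. The documents give no m, so 2 to 12 is used.

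**Formulas.**
- Risk by t months with continued dosing: F × (1 − 0.5^(t/5)). At 6 months this is 0.565F (15.2% or 27.1%); at 12 months 0.81F (21.9% or 38.9%).
- Crude on-drug percentage: F × λ/(λ+μ), with λ = ln2/5 and μ = ln2/m, which simplifies to F × m/(m+5). For m = 3 and F = 48%: 0.48 × 3/8 = 18.0%.
- Share still on drug at 5 months, ignoring stops for vascular events: 0.5^(5/m).

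| m (months) | On drug at 5 months | Crude, F=27% | Crude, F=48% | Crude ÷ 6-month risk | Crude ÷ 12-month risk |
|---|---|---|---|---|---|
| 2 | 18% (13/74) | 7.7% | 13.7% | 0.51 | 0.35 |
| 3 | 31% (23/74) | 10.1% | 18.0% | 0.66 | 0.46 |
| 4 | 42% (31/74) | 12.0% | 21.3% | 0.79 | 0.55 |
| 6 | 56% (42/74) | 14.7% | 26.2% | 0.97 | 0.67 |
| 9 | 68% (50/74) | 17.4% | 30.9% | 1.14 | 0.79 |
| 12 | 75% (55/74) | 19.1% | 33.9% | 1.25 | 0.87 |

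The ratios do not depend on F.

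**Sensitivity to the model.** With a constant hazard set to give 27% or 48% at 12 months, crude ÷ 6-month risk is 0.48-0.49 (m=2), 0.68-0.70 (m=3), 0.86-0.90 (m=4) and 1.15-1.27 (m=6). Crude ÷ 12-month risk is 0.26-0.50 for m = 2-4, and reaches 1.01-1.16 at m = 12.

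**Can the risk be estimated?** In 4,000 simulated trials (n=74, F=48%, m=3), a life table in 28-day intervals with patients at risk as denominators averaged 27.0% at 6 months (SD 7.5 points), against a true 27.1%. The crude percentage averaged 18.1%. About 13.5 patients per trial were still at risk at 6 months.

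**Follow-up after stopping.** Complete capture for one further month (F=48%, m=3) raises the crude figure from 18.0% to 21.9%, still below 27.1%.

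**DLT window.** The share of onsets within 28 days is 1 − 0.5^(0.92/5) = 12%, or 3.2% (F=27%) to 5.8% (F=48%) of patients. In 12 patients, 0.4 to 0.7 vascular events are expected. The chance that vascular events alone reach 3 of 12 is 0.6% to 2.8%.

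**The case against.** Four stronger readings are tempting, and the documents support none of them.

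- *Safety is handled by counts alone.* It is not: there is a DLT rule at each dose, review of the first 12 patients, 2-day reporting and six-monthly DSMC summaries. These are acute tolerability checks and surveillance. They do not estimate later risk.
- *The table will count continuing events repeatedly over shrinking denominators.* Section 10.3 does not say so. Section 11.1.1 defines an adverse event as something that develops or worsens, and Section 10.4 makes every treated patient evaluable. A visit is also a coarse time scale, and first events with numbers at risk at each visit would support a life table. The plan specifies neither.
- *The percentage will understate the risk because most patients stop early.* No treatment duration is documented, and direction and size depend on duration and horizon. A crude percentage is also a valid description of risk over the exposure received; the error lies in reading it as risk with continued dosing.
- *The table would mislead the choice between 30mg and 45mg.* The stated triggers for dose changes are DLTs, pharmacodynamic modulation and responses, not this table.

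The inputs are also soft. The 27% and 48% are themselves crude proportions with no horizon. The 5-month median comes from haematologic patients, and events can occur within 2 weeks. The DLT calculation isolates vascular events, whereas the rule also counts other related toxicity.

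Precision is the best argument against a heavier analysis. Only 13 patients are initially planned at 30mg, all in the RET cohort. At the crude rates for m = 2-4, that is 13 × 0.077 = 1.0 to 13 × 0.213 = 2.8 events, too few for a curve by dose. This argues for a descriptive presentation, not for leaving the analysis out.

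**Conclusion.** The gap is real but narrow. Section 10.3 has one summary method for adverse events, and no planned analysis gives per-patient, time-based or exposure-adjusted incidence of vascular occlusive events. The size is conditional: at an assumed median of 2-4 months on drug, the crude percentage is 0.51-0.79 of the 6-month risk and 0.35-0.55 of the 12-month risk. At about 6 months the two roughly agree at the 6-month horizon, and beyond that the crude figure can exceed the 6-month risk. These ratios rest on exponential onset and stopping, on independence between the two, and on a leukaemia onset time carried over to lung cancer. They show why exposure must be reported; they do not predict the bias in this trial. The plan should be amended, though the omission does not affect the primary response analysis.

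**What to change.** In Section 10.3 and the synopsis:

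- Report the number and percentage of treated patients with a first vascular occlusive special-interest event, using the Section 11.1.3 list as one composite, then arterial and venous separately.
- Give total time on drug and events per 100 patient-months.
- Show one cumulative incidence curve from first dose across all treated patients (Aalen-Johansen, death as competing event), with numbers at risk and 95% intervals. Define the follow-up window and state how patients who stop drug are censored.
- Show patient counts, exposure and rates by starting dose descriptively, noting that dose is confounded with biomarker cohort and that precision is low.
- Tabulate other adverse events per patient by worst grade.
- Include the vascular summary in the existing six-monthly DSMC report, and record new vascular events at the 30-day visit where it takes place.

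The cost is SAP wording, one table and one figure, plus one item to record at a visit that is already recommended. Vascular events are already reported under Section 11.7.2. The downside is wide intervals: only about 13 to 31 of 74 patients would still be on drug at 5 months if the median is 2-4 months.
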